8.1.4 Supportive analyses of the primary efficacy variable

Unless otherwise specified, the following supportive analyses planned for the primary efficacy endpoint will be conducted on the RS (except analyses described in [Sections 8.1.4.1](#), [8.1.4.2](#) and [8.1.4.8](#)). For the below analyses, unless specified:

- the same model as the one specified for the primary analysis will be used
- the same statistics will be provided: the mean proportion of responders (on imputed datasets when applicable) the adjusted responder rates for each treatment group, the adjusted ORs for the comparison BKZ versus placebo and its 95% CI, the p-value for the comparison between BKZ and placebo and the difference of response rates between BKZ and placebo and its corresponding 95% CI

The adjusted OR and 95% CI for the comparison BKZ versus placebo obtained from the primary analysis and from the supportive analyses described below (except for [Section 8.1.4.4](#)) will be displayed in a forest-plot.

8.1.4.1 Analysis on the PPS

The primary analysis described in [Section 8.1.2](#) will be repeated based on the PPS to evaluate the effect of IPD on the analysis.

8.1.4.2 Analysis on the FAS

The primary analysis described in [Section 8.1.2](#) will be repeated for all subjects in the FAS to evaluate the consistency between the RS and the more restrictive FAS. This analysis will only be produced if the number of subjects in the RS and FAS differs.

8.1.4.3 Analysis using modified composite estimand where intercurrent events are defined as discontinuation due to AE or Lack of efficacy

The modified composite estimand for this analysis is detailed below

- Population = Subjects enrolled according to the protocol-specified inclusion/exclusion criteria and randomized to IMP.
- Subject-level outcome = ACR50 at Week 16.
- Intercurrent event handling = An intercurrent event is defined as discontinuation due to AE or lack of efficacy. A composite strategy will be implemented in which a positive clinical outcome is defined as achieving ACR50 at Week 16 and not discontinuing study treatment due to an AE or lack of efficacy through Week 16.
- Population-level summary measure = Conditional OR comparing BKZ to placebo.

Any missing data at Week 16 that is not preceded by an IE will be imputed based on a predefined MI model (MI/MCMC - Monotone Regression) ([Section 4.2.2.2](#)).

The following categories of subjects will enter the MI/MCMC – Monotone regression process for each ACR component:

- Subjects with all post-Baseline values missing.
- Subjects withdrawn from the study treatment (data collected prior to the treatment withdrawal will be retained) - Those subjects will have values imputed for missing assessments and non missing assessment falling after study treatment discontinuation (falling after or before the study withdrawal).
- Subjects with missing value at Baseline. MI will be applied for each of the components separately before deriving the response.

In the case of partial missing data, ACR will be derived as in [Section 8.1.1](#).

If an IE occurred prior to or at week 16 (or for any other intermittent missing data at Week 16), the subjects will be considered as “non-responders”.

In MI, the missing value is replaced by a set of plausible values, where each value is a Bayesian draw from the conditional distribution of the missing data given the observed data.

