2.3 Study design and conduct

2.3.1 Study description

PA0011 is a Phase 3, multicenter, randomized, double-blind, placebo-controlled study. To be eligible to participate in this study, subjects must be adults with a diagnosis of PsA based on the Classification Criteria for Psoriatic Arthritis (CASPAR) criteria and have disease with TJC ≥ 3 and SJC ≥ 3 , as well as an inadequate response (lack of efficacy after at least 3 months of therapy

at an approved dose) or intolerance to treatment with 1 or 2 TNF α inhibitors for either PsA or PSO. Study entrance criteria are described in the protocol.

The study consists of the following periods (see [Figure 7–1](#) for a schematic diagram).

- a Screening Period (≥ 14 days to ≤ 35 days),
- a 16-week placebo-controlled Double-Blind Treatment Period,
- and a Safety Follow-Up (SFU) Period, 20 weeks after the final dose of IMP (for subjects who complete the study and do not enter the open-label extension (OLE) study or for subjects who discontinue early, including those withdrawn from IMP).

The maximum study duration per subject will be up to 37 weeks. The end of the study is defined as the date of the last visit of the last subject in the study.

[figure not shown]
Approximately 390 subjects will be randomized in a 2:1 ratio, stratified by region (North America, Western Europe, Eastern Europe, and Asia) and prior TNF α inhibitor exposure (inadequate response to 1 prior TNF α inhibitor, inadequate response to 2 prior TNF α inhibitors, or intolerance to TNF α inhibitor) to receive one of the two following blinded treatment groups:

- Bimekizumab 160mg sc Q4W,
- Placebo

Subjects discontinuing IMP during the Double-Blind Treatment Period will be encouraged to return for all scheduled visits through Week 16 and the SFU Visit, as applicable.

At the completion of the Double-Blind Treatment Period, subjects completing the study (ie, performing all visits up to Week 16 and not having permanently discontinued IMP) and who did not meet any of the withdrawal criteria will be given the opportunity to enter an OLE study at Week 16.

Figure 7–1: Study schematic diagram

ACR50=American College of Rheumatology 50% response criteria; Q4W=every 4 weeks; SFU=Safety Follow-Up; sc=subcutaneous; W=week

Refer to the clinical study protocol for more detailed information on the study assessments and schedule of procedures.

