4.2.1.3 Supportive analyses of primary efficacy endpoint

For the primary endpoint, which is a composite binary endpoint, several supportive analyses assuming different missing data mechanisms will be conducted:

- The modified composite estimand approach: the IE is changed from all treatment discontinuation to discontinuation of treatment due to AE or lack of efficacy. The same as the primary method will be used with the difference that only data after discontinuation due to AE or lack of efficacy is set to nonresponse. All other imputed data will be used.
- For the analysis of individual components of ACR, under the hypothetical estimand approach using the Reference-Based imputation method ([Section 4.2.2.3](#)).
- The tipping point approach implemented within the MI framework, but only if the primary endpoint analysis result is statistically significant at $\alpha=0.05$. ([Section 4.2.2.4](#)).
- The treatment policy strategy ([Section 4.2.2.5](#)).
- The observed case (OC) analysis that will only include the observed data. For subjects who had treatment discontinuation, only observed data prior to treatment discontinuation date will be analyzed. For visits with missing data without treatment discontinuation, the data will remain missing. For observed data after treatment discontinuation, the corresponding visit data and subsequent visit data will be treated as missing.

4.2.1.4 Supportive analyses of endpoints that are part of the testing hierarchy (secondary endpoints)

The following supportive analysis methods will be performed for the secondary and the other efficacy variables that are part of the testing hierarchy:

For binary endpoints:

- The modified composite estimand approach: the IE is changed from all treatment discontinuation to discontinuation of treatment due to AE or lack of efficacy. For composite or non-composite binary endpoints, the standard MI approach) will be implemented (similarly as in [Section 4.2.1.3](#)) on the raw continuous score(s) (eg, PASI for the PASI90 endpoint) before deriving the binary endpoint based on the imputed score(s).
- The OC analysis.

For continuous endpoints:

- The hypothetical estimand approach:
 - If subjects have missing data regardless whether the missing data is preceded by an IE, then missing data will be imputed based on the MI-MCMC/Monotone regression method ([Section 4.2.2.2](#)).
 - If subjects have non-missing data after IE, then such data will be set to missing prior to running MI.

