4.2.1.6 Summary table of missing data handling approaches for efficacy analyses

The below table summarizes which missing data handling approaches will be used for each type of efficacy endpoint.

Table 7–2: Missing data handling approaches for efficacy endpoints

Efficacy Endpoint Priority	Variable Type	Missing data handling approach						
		Composite estimand (NRI)	Modified Composite estimand (MI)	Hypothetical estimand (MI)	Hypothetical Reference-Based (MI)	OC	Tipping Point analysis (MI)	Treatment Policy (MI)
Primary endpoints	Composite Binary	P	S ^a			S	S ^a	S ^a
	Binary	P	S ^a			S		

Efficacy Endpoint Priority	Variable Type	Missing data handling approach						
		Composite estimand (NRI)	Modified Composite estimand (MI)	Hypothetical estimand (MI)	Hypothetical estimand Reference-Based (MI)	OC	Tipping Point analysis (MI)	Treatment Policy (MI)
Secondary endpoints included in the testing hierarchy	Continuous			S	P	S		
Other Secondary endpoints (not included in the testing hierarchy)	Binary	X	X ^a			X		
	Continuous			X		X		
Other endpoints	Binary	X	X ^{a,b}			X		
	Continuous			X ^b	X ^d	X		
	Categorical	X ^c	X ^c			X		

P=Primary method, S=Supportive method, X=Method to be used (no priority designated) MI= multiple imputation, NRI=non-responder imputation, OC=observed cases.

Note: Composite estimand (NRI) refers to the approach in which data preceded by the intercurrent event of study treatment discontinuation are imputed as nonresponse, and other missing data are also imputed as nonresponse.

Note: Modified Composite Estimand (MI) refers to the approach in which data preceded by the intercurrent event of study treatment discontinuation due to AE or lack of efficacy are imputed as nonresponse (or worst category for categorical variable), and other missing data are imputed via a MI model.

Note: Hypothetical Estimand (MI) refers to the approach where outcomes for subjects without an intercurrent event of study treatment discontinuation are as observed, and outcomes for subjects with the intercurrent event are imputed via a MI model.

Note: Referenced Based imputation refers to the approach in which it is assumed that the statistical behavior of the bimekizumab and placebo-treated subjects after discontinuing study medication becomes that of the placebo-treated subjects that remain in the study.

^a Imputation method is applied on continuous data, and binary variable is derived from the continuous variable based on complete imputed data set.

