4.2.2.2.1 Non-Composite binary endpoints

For non-composite binary endpoints, the MI method will be applied as follows based on raw values:

- Step 1: Imputation of missing data using MI:

Create datasets, one for each treatment group, of subjects with observed values and missing values (needing estimation by MI). For the imputation step, missing values will be separated into 2 categories: intermittent missing values (ie, missing values for a given subject that has available data before and after the missing timepoint, including missing value at Baseline) and monotone missing values (ie, where all subject data is missing after a given time point). Datasets should be designed in a horizontal structure meaning that each subject should be present in a single observation, with a set of values, one for each scheduled visit where the endpoint is supposed to be collected according to the protocol (this excludes the unscheduled visits).

Datasets should also be sorted by subject number before proceeding with the MI process.

- For the intermittent missing values**, the missing value in each dataset will be filled in using the Markov-Chain Monte Carlo (MCMC) method with multiple chains, monotone missing data imputing pattern, and non-informative priors for all parameters. Unless specified differently, the first 200 iterations will not be used (the ‘burn-in’ option). A total of 100 sets of imputations will be performed. The seed used for these imputations will be 2017 and all other MI procedures described in this SAP will use this same seed as well. The procedure will be performed for each treatment group separately.

The resulting 100 imputed data sets will have a monotone missing pattern and will be imputed using a method for monotone missingness:

- For monotone missing data**, one monotone regression will be used to impute missing data. A separate regression model is estimated for each variable with missing values (ie, measurement at each time point). Based on the resulting model, a new regression model is then drawn and is used to impute the missing values for the variable. Since the data set has a

monotone missing data pattern, the process is repeated sequentially for variables with missing values. The procedure will be based on the 100 imputed datasets generated from the MCMC procedure and will be performed for each treatment group separately by imputation.

The SAS® PROC MI procedure will be used for the imputation.

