- No improvement at Week 16 of at least 50% from baseline on TJC (regardless of whether the remaining components are missing or not)
- No improvement for at least 3 out of the 5 ACR components (PGA-PsA, PhGA-PsA, PtAAP, HAQ-DI, hs-CRP) regardless of whether the remaining components are missing or not
- Missing ACR50 response
 - For all other situations that are not specified above.

For the OC analysis: if a given visit falls after the treatment discontinuation date, the endpoint at this visit and all subsequent visits (whether the data were observed or not) will be derived but reported as missing (Section 8.1.4.6).

For the MI analysis: if a given visit falls after the treatment discontinuation date, the endpoint at this visit and all subsequent visits (whether the data were observed or not) will be imputed. Responses falling after an IE (defined as treatment discontinuation due to AE or lack of efficacy for the modified composite estimand) will be set to nonresponse (Section 8.1.4.3).

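### Modified composite analysis (SAP 8.1.4.3) replaces observed Week 16 data after discontinuation for other reasons, a hypothetical strategy its estimand does not declare

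*SAP*

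**What the plan says.** Section 8.1.4.3 gives four attributes. The intercurrent event is stated once: "An intercurrent event is defined as discontinuation due to AE or lack of efficacy". Success is ACR50 at Week 16 without that event. The section then says: "Any missing data at Week 16 that is not preceded by an IE will be imputed based on a predefined MI model". The note on this method under the missing-data table in 4.2.1.6 matches: after nonresponse is assigned following an AE or lack-of-efficacy discontinuation, "and other missing data are imputed via a MI model".

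The list of subjects entering imputation in 8.1.4.3 is broader. For all subjects withdrawn from study treatment, "Those subjects will have values imputed for missing assessments and non missing assessment falling after study treatment discontinuation". The MI paragraph of 8.1.1 says the same of a visit after the treatment discontinuation date: "the endpoint at this visit and all subsequent visits (whether the data were observed or not) will be imputed". Section 4.2.1.3 states what happens to the draws: "only data after discontinuation due to AE or lack of efficacy is set to nonresponse. All other imputed data will be used".

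On the imputation itself, 4.2.2.2 assumes data missing at random and 4.2.2.2.1 adds: "The procedure will be performed for each treatment group separately". On whether such data will exist, 2.3.1 says: "Subjects discontinuing IMP during the Double-Blind Treatment Period will be encouraged to return for all scheduled visits through Week 16".

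**The concern.** A subject who stops IMP for a reason other than AE or lack of efficacy has no intercurrent event under this estimand, and none of the four attributes gives a strategy for that case. An ACR50 status observed at Week 16 is then the outcome the estimand asks for. The procedure sets it aside and substitutes a prediction built from on-treatment data in the same arm, which answers what would have happened had treatment continued.

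Two things are at stake. First, the odds ratio goes into the forest plot described in 8.1.4 beside the primary result, labelled as an estimand it does not target. Second, 8.1.4.3 contains both rules. Its sentence on missing data and the note in 4.2.1.6 lead to keeping observed values; its list of subjects and 8.1.1 lead to overwriting them. Section 8.2.3 carries the method to PASI90 and MDA.

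**Working it through.** **1. Who keeps drawn values in place of observed ones**

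| Reason for stopping IMP | Intercurrent event in 8.1.4.3? | Observed Week 16 value under the stated estimand | Under the procedure |
|---|---|---|---|
| AE or lack of efficacy | Yes | Nonresponse | Imputed, then reset to nonresponse |
| Any other reason | No | Used as observed | Replaced by a draw, and the draw is kept |

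Section 8.1.1 separates treatment discontinuation, which triggers imputation, from the narrower intercurrent event, which triggers nonresponse. The overwriting therefore covers every reason for stopping, and the two readings differ only in the second row.

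**2. Which of these subjects are reached**

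Section 3.4 dates discontinuation at treatment end plus 31 days. With first dose on Day 1, the nominal Week 16 visit is Day 113, with a window of ±3 days (Day 110 to 116).

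- Last dose Baseline: 1 + 31 = Day 32, before Week 16.
- Last dose Week 4: 29 + 31 = Day 60, before Week 16.
- Last dose Week 8: 57 + 31 = Day 88, before Week 16.
- Last dose Week 12: 85 + 31 = Day 116, the last day of the window, so a visit in window does not fall after it.

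The group is therefore mainly subjects last dosed at about Week 8 or earlier, for another reason, who still attended Week 16.

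**3. Planning figures**

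Section 2.4.1 assumes ACR50 of 26% on BKZ (n = 260) and 10% on placebo (n = 130). The odds ratio is (0.26/0.74) / (0.10/0.90) = 3.16, as stated. The stated 96% power also reproduces (96.6% with continuity correction); it is not in question here.

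**4. Illustration of size (assumed inputs)**

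The SAP gives no rate for the affected subjects. Let *s* be their share in each arm, *r* their observed BKZ response, and let the draws return the arm rates.

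- BKZ rate, observed data kept: (1 − s) × 0.26 + s × r
- Placebo rate, observed data kept: (1 − s) × 0.10 + s × min(r, 0.10)
- Shift in the BKZ rate from overwriting: s × (0.26 − r)

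| s | r | Affected BKZ subjects | BKZ rate, kept | Shift (points) | Difference, kept (points) | OR, kept |
|---|---|---|---|---|---|---|
| 2% | 15% | 5.2 | 25.78% | 0.22 | 15.8 | 3.13 |
| 4% | 10% | 10.4 | 25.36% | 0.64 | 15.4 | 3.06 |
| 8% | 10% | 20.8 | 24.72% | 1.28 | 14.7 | 2.96 |
| 8% | 5% | 20.8 | 24.32% | 1.68 | 14.7 | 3.03 |

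After overwriting, the figures are 26.0%, 16.0 points and 3.16 throughout. Over s = 2–8% and r = 5–15%, the shift is about 0.2 to 1.7 points.

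The sign comes from the assumptions. The shift is zero at r = 26% and reverses above it: at s = 8% and r = 30% it is 0.08 × (0.26 − 0.30) = −0.32 points.

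**The case against.** The best defence is that the overwriting is deliberate and pre-specified. Section 3.7 restricts efficacy data collected after treatment discontinuation to listings, with the treatment policy analysis as the only exception, and 8.1.1 and the list in 8.1.4.3 apply that rule. This stands as an account of intent. It also means that keeping the observed values requires a change to 3.7. It does not repair the estimand, which still has no strategy for these discontinuations, or the note in 4.2.1.6.

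Second, the off-treatment outcomes are not lost. The treatment policy analysis in 8.1.4.5 uses them and reports the observed ACR50 responses, its odds ratio is in the same forest plot, and the primary analysis counts every discontinuation as nonresponse. This stands and limits the weight of the point.

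Third, a reader might infer that the analysis favours BKZ by assuming continued benefit after the drug is stopped. The documents do not support that:

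- Each draw conditions on the subject's own Baseline and earlier visits (4.2.2.2.1), so a subject doing poorly before stopping tends to be imputed poorly. The draws need not return 26%.
- Sections 5.1 and 10.1.1 equate 140 days with five half-lives, or 28 days each. A subject last dosed at Week 8 is 56/28 = 2 half-lives out at Week 16, and 8.1.4.5 allows for other medication. Off-treatment response may exceed the placebo rate.
- Placebo discontinuers are overwritten too.

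**Conclusion.** The mismatch is established from the text. As specified, the modified composite analysis applies a hypothetical strategy to discontinuation for other reasons that its estimand does not declare, so it does not estimate that estimand for ACR50, or for PASI90 and MDA where the same method is used.

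Neither the direction nor the size of the effect can be derived from the SAP. The range of 0.2 to 1.7 points on the BKZ rate (odds ratio 2.96 to 3.13 against 3.16) rests wholly on assumed shares of 2–8%, assumed off-treatment response of 5–15% on BKZ and at most 10% on placebo, and draws equal to the planning rates. It shows scale and is not evidence of bias towards BKZ.

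Severity is low. The analysis is supportive and outside the testing hierarchy, the group reached is narrow, and the primary and treatment policy results do not change.

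**What to change.** Choose one and make the text agree.

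- **To match the stated estimand:** keep observed Week 16 data of subjects who stopped for reasons other than AE or lack of efficacy, and impute only data that are truly missing. Amend the list of subjects in 8.1.4.3 and the MI paragraph of 8.1.1, and add this analysis to the exception in 3.7. The cost is SAP wording and a small programming change; some off-treatment values will enter the analysis.
- **If the overwriting is intended:** name discontinuation for other reasons in 8.1.4.3 as a second intercurrent event with a hypothetical strategy, and correct the note in 4.2.1.6 to say that observed values after such discontinuation are also imputed. The cost is wording only, and the forest-plot estimate is then labelled as what it is.

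Either way, the choice should carry through to PASI90 and MDA in 8.2.3.

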In both cases, the imputation model will include the randomization strata as stratification variables (region and prior TNF α inhibitor exposure), the value at Baseline and at each post-Baseline visit (up to the week of interest). The imputation model based on the MCMC method will only allow joint multivariate normal variables. For the MCMC method (when imputing intermittent missing values), randomization strata will be re-coded as indicator variables, and will be always specified in the following order if they are retained in the model:

- North America region (1 for North America, 0 otherwise)
- Western Europe region (1 for Western Europe, 0 otherwise)
- Eastern Europe region (1 for Eastern Europe, 0 otherwise)
- Prior TNF α 1 (1 for inadequate response to 1 prior TNF α inhibitor)
- Prior TNF α 2 (1 for inadequate response to 2 prior or more TNF α inhibitors)

No variable needs to be created for the 3rd category of prior TNF α inhibitors (intolerance to TNF α inhibitors) or the 4th region (Asia) which is covered when all above variables are “0”.

The randomization strata (region and prior TNF α inhibitor exposure) may be dropped from the imputation model to facilitate model convergence if required (this will be the case for all imputation models) as described below:

- If the MI fails to converge when adjusting on the stratification variables specified above, or if the percentage of randomized subjects is less than 10% in either of the Asia or Western Europe regions, then the Western Europe and Asia region will be combined and the binary variables for region that will be left in the MI will then be for North America and Eastern Europe regions.
- If after doing that, the MI still fails to converge then all region factors will be removed from the MI.
- If the MI still does not converge after dropping the regions, the remaining stratification variables (Prior TNF α 2,1) will also be removed.
- If a variable is dropped in order to allow convergence for one model in the study, that variable does not have to be dropped from other models in the study of the model converges without dropping the variable. That is, model convergence should be evaluated for each efficacy table independently. Furthermore, this means that a table based on a single timepoint may have different variables in the imputation model than a separate by-visit table for the same variable.

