8.1.2 Primary analysis of the primary efficacy variable

The primary efficacy variable will be analyzed for all subjects in the RS.

The primary endpoint is the ACR50 response at Week 16. The primary efficacy analysis will evaluate the composite estimand in the RS. The composite estimand combines the clinically meaningful improvement from Baseline in ACR components as assessed using the ACR50 response at Week 16 and not discontinuing study treatment prior to Week 16.

The following 4 attributes describe the estimand that will be used to define the treatment effect of interest for the primary efficacy analysis:

- Population = Subjects enrolled according to the protocol-specified inclusion/exclusion criteria and randomized to IMP
- Subject-level outcome = ACR50 at Week 16
- Intercurrent event handling = An intercurrent event is defined as discontinuation of study treatment prior to Week 16. A composite strategy will be implemented in which a positive clinical outcome is defined as achieving ACR50 at Week 16 and not discontinuing study treatment through Week 16.
- Population-level summary measure = Conditional odds ratio comparing BKZ to placebo and difference of response rate between BKZ and placebo.

Missing data at Week 16 that are not preceded by an IE and any data after an IE will be imputed as non-responders. This results in a more traditional NRI approach and will be labeled as such throughout the SAP.

The statistical hypothesis for the ACR50 response at Week 16 is that the conditional OR for ACR50 response in the BKZ treatment compared to placebo treatment is equal to 1.

A logistic regression model will be used to assess the treatment effect on ACR50 response at Week 16. The model will include fixed effects for treatment, and prior TNF α inhibitor exposure and region as stratification factors. The suitability of including these variables in the model will be assessed using Pearson and Deviance and the Hosmer-Lemeshow Goodness-of-Fit Tests (Hosmer and Lemeshow, 2000).

P-values below 0.05 would lead to a reconsideration of the model to be used and if the logistic regression model is unable to converge the stratification variables will be dropped ([Section 4.1](#)). In that case, all supportive analyses as well as imputation models conducted for the primary endpoint will disregard these exploratory factors from their models.

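### Section 8.1.4.3 of the SAP gives two opposite rules for subjects with no intercurrent event and missing Week 16 data: multiple imputation, and non-response by a stray parenthesis

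*SAP*

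**What the plan says.** SAP Section 8.1.4.3 describes a supportive analysis of ACR50 at Week 16 under a narrower IE than the primary analysis uses: "An intercurrent event is defined as discontinuation due to AE or lack of efficacy".

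The section then gives two rules for missing Week 16 data:

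- **Rule A:** "Any missing data at Week 16 that is not preceded by an IE will be imputed based on a predefined MI model".
- **Rule B:** a subject is a non-responder if an IE has occurred by Week 16, "or for any other intermittent missing data at Week 16".

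Between the two rules is a list of subjects who enter the imputation. It names those with no post-Baseline values, those withdrawn from study treatment, and those with a missing Baseline value. It does not name a subject still on treatment who has earlier post-Baseline data but lacks Week 16.

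Other sections describe the same analysis. Section 4.2.1.3 says that "only data after discontinuation due to AE or lack of efficacy is set to nonresponse. All other imputed data will be used". The note on this estimand under the missing-data summary table in Section 4.2.1.6 makes post-IE data non-response, "and other missing data are imputed via a MI model".

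**The concern.** Take a subject who stays on treatment and whose Week 16 ACR50 cannot be derived. There has been no IE, so Rule A imputes the outcome. Read naturally, the words in Rule B about any other missing data at Week 16 make the same subject a non-responder. Both rules are in the current text, a few lines apart.

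The purpose of the analysis is to relax the primary rule, under which "Missing data at Week 16 that are not preceded by an IE and any data after an IE will be imputed as non-responders". Programmed literally, Rule B brings that rule back for on-treatment missing data. The supportive analysis would then differ from the primary one only for subjects who discontinue for reasons other than an adverse event or lack of efficacy.

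The wording also reaches further than ACR50. Section 8.2.3 runs the supportive analysis of the secondary binary endpoints as in Section 8.1.4.3, which includes PASI90 and MDA from the testing hierarchy. For those two, the summary table lists only this method and observed cases as supportive approaches.

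**Working it through.** **Step 1. Can a Week 16 value be intermittent?** Section 4.2.2.2.1 defines intermittent missing values as "missing values for a given subject that has available data before and after the missing timepoint, including missing value at Baseline". The same section says that the imputation model stops at the week of interest, here Week 16. No later value enters the model, so a missing Week 16 value has nothing after it and cannot be intermittent. The parenthesis in Rule B therefore applies to nobody under the definition, or, if read loosely, to on-treatment missing data, which Rule A imputes.

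**Step 2. Which rule does the rest of the SAP support?**

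| Place | Who is set to non-response | Other missing Week 16 data |
|---|---|---|
| 8.1.4.3, Rule A | not addressed | MI |
| 8.1.4.3, Rule B | IE, plus the parenthesis | non-response if read loosely |
| 4.2.1.3 | only data after an IE | imputed values used |
| 4.2.1.6, table note | data after an IE | MI |
| 4.2.2.2, composite binary endpoints, Step 3 | subjects with an IE | imputed values used |
| 8.1.1, paragraph on the MI analysis | responses after an IE | not set to non-response |

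The parenthesis is the only outlier.

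**Step 3. Planning figures reproduced.** Inputs from Sections 2.4 and 2.4.1: 26% versus 10%, 260 versus 130 subjects, two-sided 0.05, chi-square test with continuity correction, stated power 96%, stated odds ratio (OR) 3.16.

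- OR = (0.26/0.74) / (0.10/0.90) = 3.16, as stated.
- With k = 2, d = 0.16 and p̄ = (0.10 + 2 × 0.26)/3 = 0.2067, the uncorrected placebo group size is n = [1.96 √(p̄(1 − p̄)(1 + 1/k)) + z √(0.10 × 0.90 + 0.26 × 0.74/k)]² / d². The corrected size is (n/4)[1 + √(1 + 2(1 + 1/k)/(n d))]². Setting this to 130 gives n of about 120.8 and power 96.6%, in line with the stated 96%. Without the correction the power is 97.6%.

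The contradiction does not touch these figures. They serve only as the base for Step 4.

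**Step 4. Size of the gap between the two rules.** The SAP gives no on-treatment missing rate, so the share m is an assumption. MI is taken to return the planning rates. Rule A then gives 26% and 10%. Rule B gives 26% × (1 − m) and 10% × (1 − m). With equal m, the difference shrinks by m × 16 points.

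| m, BKZ / placebo | Rule B rates | Difference | Shift from 16.0 points | OR |
|---|---|---|---|---|
| 2% / 2% | 25.5% vs 9.8% | 15.7 | 0.3 | 3.15 |
| 5% / 5% | 24.7% vs 9.5% | 15.2 | 0.8 | 3.12 |
| 10% / 10% | 23.4% vs 9.0% | 14.4 | 1.6 | 3.09 |
| 5% / 10% | 24.7% vs 9.0% | 15.7 | 0.3 | 3.32 |
| 10% / 5% | 23.4% vs 9.5% | 13.9 | 2.1 | 2.91 |

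The same arithmetic applies to the planning differences in Section 2.4.2, which are 28 points for PASI90 and 12 points for MDA. With equal shares of 2% to 10%, PASI90 shifts by 0.02 × 28 = 0.6 to 0.10 × 28 = 2.8 points. MDA shifts by 0.02 × 12 = 0.2 to 0.10 × 12 = 1.2 points.

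**The case against.** The strongest reply is that the SAP already settles the matter. A programmer who applies its definition of intermittent would set nobody to non-response under the parenthesis, and four other places, together with Rule A, point to MI. On that view the words are harmless. This largely stands as a guide to what was intended. It does not make the text sound: a clause that is either empty or contradictory should not remain in an analysis specification, and the list of subjects entering MI does not rescue it, because it leaves out the very subjects in question.

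A reader might infer more than the document supports:

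- **That this is the main sensitivity analysis of the primary endpoint.** The SAP does not rank its supportive analyses. For ACR50 the tipping point, treatment policy and observed-case analyses stand beside it.
- **That under Rule B it would nearly repeat the primary analysis.** Discontinuations for other reasons would still be imputed here but are non-response in the primary analysis. The SAP gives no split between such discontinuations and on-treatment missingness, so the closeness of the two results is unknown.
- **That every remote COVID-19 visit at Week 16 would be affected.** Section 5.2 expects joint counts and CRP to be missing at remote visits. Under Section 8.1.1, however, ACR50 is still an observed negative when at least three of the five other components have not improved. Only some of these visits would yield a missing response.

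**Conclusion.** Section 8.1.4.3 contradicts itself for subjects with no IE and missing Week 16 data, and the parenthesis is the part that is wrong as written. The point concerns wording in one supportive method, which is reused for the secondary binary endpoints. The primary analysis, the testing hierarchy and its error control are unaffected.

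For ACR50 the two rules would move the response difference by about 0.3 to 1.6 points. This rests on two assumptions that the SAP does not supply: 2% to 10% on-treatment missing data equally in both arms, and MI that preserves the planning rates. Unequal missingness could move the odds ratio either way, to 2.91 or 3.32 in the two cases tried, against 3.16. The effect is modest, but leaving two rules in place lets the result depend on which sentence is programmed.

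**What to change.** Make two edits to Section 8.1.4.3:

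1. Delete the parenthesis, so that only subjects with discontinuation due to an adverse event or lack of efficacy by Week 16 are set to non-response.
2. Add to the list of subjects entering MI those still on treatment whose Week 16 component data are missing. Deleting the parenthesis alone would leave them outside the list.

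This brings the section into line with Sections 4.2.1.3, 4.2.1.6, 4.2.2.2 and 8.1.1. Section 8.2.3 follows by cross-reference. The cost is two short text changes and a check that the program matches them. The imputation is already planned, and no new data or change in sample size is needed.
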